The dietary program and intervention materials will be developed and delivered by employees of Pennington Biomedical Research Center (PBRC). Outcome assessors will be blind to diet assignment and genotype pattern. Interventionists will be blind to genotype pattern, but not diet type. To enhance internal validity, participants will not be told if they are carbohydrate or fat responders until after they complete the study. The **primary outcome** variables are weight change (kg and %) over 12 weeks. All other measures are secondary endpoints. The schedule of procedures is provided in **Table 2**.

**Table 2.** Schedule of visits and procedures.

	Orientation	Baseline (Week 0)	Week 6**	Week 12
Location	IBL	Clinic	IBL	Clinic
Consent, eligibility, demographics, medical history form	X			
Height	X			
Weight	X	X	X	X
Genealogy test kit	X			
Waist/hip circumference, bioelectrical impedance analysis, blood pressure, heart rate, Food Craving Inventory, Food Preference Questionnaire, Eating Inventory		X		X
Blood draw: fasting serum glucose, insulin		X		
Randomization		X		
Intervention Satisfaction Survey				X
Diet Personalization Survey (completed after randomization and at week 6 and 12)		X	X	X
* There is no clinic visit at week 6. The week 6 weight will be collected at the participants' intervention visit, where participants will also complete the Diet Personalization Survey. If participants miss this visit, they will complete the Diet Personalization Survey during the next intervention visit.				
** Weight will be collected at each of the 12 intervention visits.				

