### **Data analytic plan**

The biostatistics department will handle the randomization and use adaptive randomization to promote equal numbers of men and women in each cell and to promote similar BMI across the groups.

The primary outcome variable is body weight change, represented as kg and percent change. All other variables are secondary and will be analyzed using a similar statistical approach. Repeated mixed linear models will be used to determine if change in the outcome variables differs among the groups. Covariates will include the baseline value of the outcome, sex, and race. Additional variable selection in the models will be determined through model fit statistics such as AIC.

Two sources of body weight data are obtained – weights collected in the clinic at baseline and week 12, and weights collected at the 12 intervention sessions. Both sources of data will be analyzed, though the presence of only two clinic weights means that analysis of the clinic weights will be a completers' analysis. The weekly weight data, however, will be analyzed using an intent-to-treat approach, and all participants' data will be analyzed who have a weight from their first and at least one subsequent intervention visit. Sensitivity analysis will be conducted to determine how the two methods effects the results.

The primary models will be a mixed effect model that accounts for the correlation of the subject over time modeling. Least square means based on the estimates from the mixed effect model will be used to test for differences of weight change between groups. Normality of the responses will be checked based on the Shapiro-Wilk test. Heterogeneity of variance effects for genders for each of the treatments will be analyzed first as potential subgroups.

Hypothesis 1 will test if participants assigned to the diet that corresponded to their genotype lost more weight than those assigned to a diet inconsistent with their genotype.

- H1: Weight loss in Cells A and D (combined) in Table 1 was significantly larger than weight loss in Cells B and C (combined).

Hypothesis 2 will analyze the fat responders and carbohydrate responders separately.

- H2a: Fat responders lost more weight on the high-fat diet (Table 1, Cell A) vs. the high-carbohydrate diet (Cell B), and
- H2b: Carbohydrate responders lost more weight on the high-carbohydrate diet (Table 1, Cell D) vs. the high-fat diet (Cell C).

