The *a priori* comparisons noted above will rely on an alpha level of 0.05 for both measures of body weight (kg and %). In addition, we will conduct tests with alpha equal to 0.05 to determine if baseline insulin levels and HOMA (homeostatic model assessment) are associated with weight loss and differential weight loss between the groups and diets. Alpha will be adjusted in the analyses of all other variables using the family-wise error rate employing the Holm-Bonferroni method, which is based on the number of p-values less than alpha.

The Report to the sponsor will include data tables for all outcome variables at all assessment visits, as well as tables depicting change on the outcome variables and the associated inferential statistics. Tables depicting participant demographics will also be provided.

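### The stated basis for the Holm-Bonferroni adjustment of secondary outcomes is wrong: Holm uses the total number of tests, not the number of p-values below alpha

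*Combined protocol and SAP*

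**What the plan says.** The Data analytic plan tests the weight comparisons (kg and percent) and the baseline insulin/HOMA associations at 0.05 each, outside any adjustment. For everything else it states: "Alpha will be adjusted in the analyses of all other variables using the family-wise error rate". The same sentence goes on to name the procedure and to say what it rests on: "employing the Holm-Bonferroni method, which is based on the number of p-values less than alpha".

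Membership of that family is defined by exclusion. The Background section, after naming weight change as primary, says "All other measures are secondary endpoints". The Data analytic plan adds "All other variables are secondary and will be analyzed using a similar statistical approach". Table 2 lists the repeated measures: "Waist/hip circumference, bioelectrical impedance analysis, blood pressure, heart rate, Food Craving Inventory, Food Preference Questionnaire, Eating Inventory" at baseline and week 12, and the Diet Personalization Survey also at week 6. The Intervention Satisfaction Survey is given at week 12 only. The number of tests is not stated.

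The report to the sponsor is to contain outcome tables at each assessment, "as well as tables depicting change on the outcome variables and the associated inferential statistics".

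**The concern.** Holm orders the m p-values in the family and compares the smallest with alpha/m, the next with alpha/(m−1), and so on, stopping at the first failure. Here m counts every hypothesis in the family, whether or not its p-value is small. Family-wise control depends on this.

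The plan ties the method instead to the count of p-values below alpha, which depends on the data. If that count takes the place of m, the penalty is smallest when few results are nominally significant, and it vanishes when there is exactly one. The sentence therefore promises family-wise control by a named method and then describes something that does not deliver it. Nothing elsewhere in the document corrects it.

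At stake is how the secondary results in the sponsor report are read. They could be taken as family-wise controlled when the procedure behind them is close to no adjustment.

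**Working it through.** The plan gives neither a family-wise error rate nor m, so it has no figure to reproduce. The benchmark is the promised control, at an assumed alpha of 0.05 (the level the plan uses for its other tests).

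**Rules compared**
- Standard Holm: thresholds 0.05/m, 0.05/(m−1), …
- Rule as written: the same step-down with K, the number of p-values below 0.05, in place of m.
- No adjustment: each test at 0.05.

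**Single case.** Ten tests, one with p = 0.02 and the rest above 0.05. Standard Holm: 10 × 0.02 = 0.20, not significant (equivalently 0.02 > 0.05/10 = 0.005). Rule as written: K = 1, so 1 × 0.02 = 0.02, significant.

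**Exact error rate, independent tests, all nulls true.**
- K follows a Binomial(m, 0.05) distribution. Given K = k, those k p-values are uniform on (0, 0.05), so at least one rejection occurs with probability 1 − (1 − 1/k)^k.
- Rule as written: FWER = Σ(k≥1) P(K=k) × [1 − (1 − 1/k)^k].
- For m = 10, k = 1 to 4: 0.3151 × 1 + 0.0746 × 0.75 + 0.0105 × 0.704 + 0.0010 × 0.684 + … = 0.379.
- Standard Holm: 1 − (1 − 0.05/10)^10 = 0.049.
- No adjustment: 1 − 0.95^10 = 0.401.

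| m | As written | Standard Holm | No adjustment |
|---|---|---|---|
| 3 | 0.141 | 0.049 | 0.143 |
| 5 | 0.221 | 0.049 | 0.226 |
| 10 | 0.379 | 0.049 | 0.401 |
| 20 | 0.572 | 0.049 | 0.642 |
| 30 | 0.664 | 0.049 | 0.785 |

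**Correlated tests.** Outcomes measured on the same people are correlated, so the rates were also simulated with two-sided normal tests and a common correlation between variables.
- *10 tests* (assumed): one score and one contrast for each of waist, hip, body fat %, systolic pressure, diastolic pressure, heart rate, the three eating questionnaires and the Diet Personalization Survey; 400,000 runs.
- *30 tests* (assumed): the same ten variables with three contrasts each, namely A−B, D−C and their sum weighted 52:25 from the cell sizes in Table 1; 200,000 runs. The contrasts overlap, so the rate at correlation 0 is below the independent value of 0.664.

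| Tests | Rule | 0 | 0.3 | 0.5 | 0.8 |
|---|---|---|---|---|---|
| 10 | As written | 0.378 | 0.327 | 0.260 | 0.131 |
| 10 | Standard Holm | 0.048 | 0.045 | 0.039 | 0.023 |
| 10 | No adjustment | 0.400 | 0.351 | 0.287 | 0.173 |
| 30 | As written | 0.578 | 0.518 | 0.428 | 0.225 |
| 30 | Standard Holm | 0.043 | 0.041 | 0.036 | 0.022 |
| 30 | No adjustment | 0.702 | 0.635 | 0.539 | 0.348 |

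Adding the Intervention Satisfaction Survey (11 tests) changes little: as written 0.404, 0.347, 0.272 and 0.132.

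**The case against.** The best defence is that the operative instruction is the named method. Holm-Bonferroni is a complete, standard specification, an analyst would normally run it on all p-values, and the trailing clause is description rather than formula. It may be a loose reference to the step-down feature, since Holm's divisor does fall as hypotheses are rejected. Nothing in the document shows that standard Holm will not be run. This stands as far as it goes: under that reading error control is intact and only the wording needs correcting. It does not rescue the clause. The divisor falls with the number already rejected, starting from m; it is not set by the number of p-values below alpha. Passing only the p-values below 0.05 to a Holm routine is a plausible way to carry out the sentence, and the two readings give different answers.

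The error rates are also conditional on an assumed m, assumed correlations and all nulls being true. That is correct, and the zero-correlation figures are upper-end illustrations. Even so, at correlation 0.8 the rule as written gives more than twice 0.05.

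Finally, the family is less open than the missing count suggests. Table 2 fixes the assessment times, and the reference to a similar approach points to the same contrasts as for weight. This also stands. What remains open is the scores or subscales per instrument, the exact contrasts, and which times are tested where there are more than two. That is missing detail, separate from the error in the clause.

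**Conclusion.** The concern holds and should be fixed. The description of Holm-Bonferroni is wrong as written and conflicts with the family-wise control promised in the same sentence. That conclusion needs no assumption about m.

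The consequence depends on implementation. With standard Holm the family-wise rate stays at or below 0.05 and the defect is one of wording. With the count of small p-values in place of m, control is lost: 0.13 to 0.38 for 10 tests and 0.22 to 0.58 for 30, over correlations from 0.8 down to 0. For 10 independent tests this is nearly the same as no adjustment. These figures assume alpha 0.05, all nulls true and the stated test counts.

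The reach is limited to the secondary variables. The three weight hypotheses (H1, H2a, H2b) and the insulin/HOMA tests lie outside this adjustment.

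**What to change.** Replace the clause with: Holm step-down, with m equal to the total number of pre-specified tests in the family, regardless of how many p-values are below 0.05. This correction is sufficient on its own to resolve the contradiction.

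Alongside it, list the tests that make up m: each variable, the score or subscales used from each questionnaire, the contrasts, and the time points. Even correctly coded Holm needs m, and fixing it in advance prevents the count being chosen after the p-values are seen.

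The cost is one clause and one list. Data collection and the primary tests do not change. No power is lost against the Holm adjustment the plan already promises; there would be fewer significant secondary results only in comparison with the rule as written.

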### **Recruitment Methods**

The marketing and the recruiting core will utilize traditional PBRC recruiting methods. The Advertising and Recruitment Cores are responsible for recruiting potential participants for clinical trials from a population that includes a wide range of people of various ages, ethnic backgrounds and with varying degrees of health. PBRC has a team of full-time employees dedicated to the recruitment and initial screening of clinical trials. Potential subjects will be identified via a large database of previous study participants along with the use of web, print, and media advertising. The Recruitment and Advertising Cores create and implement individualized, trial-specific advertising and awareness campaigns, including mass media, traditional advertising, and novel methods including social media, digital and email marketing. All advertising and awareness are approved by our on-site IRB to ensure ethical and disclosure standards are met. The PBRC database will also be utilized to find potential subjects for this study.

### **Study Procedures**

The study consists of an orientation visit, and if participants are eligible and wish to participate, two clinic visits (one before and one after the intervention), and 12-weekly intervention visits.

#### Orientation Visit: About 1 hour.

The orientation visit will take place at Pennington Biomedical Research Center and it will include the following procedures:

- Informed consent
- Questionnaires assessing medical history, current medication and supplement use, and demographics
- Measurement of height and weight
- If participants have completed a genealogy test before the study, their data will be reviewed to verify eligibility to participate in the study
- If participants have NOT completed a genealogy test before the study, they will be provided with a genealogy test kit and the data will be reviewed as soon as they are available to us to determine eligibility to participate in the study

Baseline Clinic Visit: About 1.5 hours.

If participants are eligible and wish to participate in the study, the first clinic visit will be scheduled. The visit will take place in the Outpatient Clinic of Pennington Biomedical Research Center. *This is a fasting visit (nothing to eat or drink before the visit, following a 12-hour fast).* The clinic visit will include the following procedures:

- Measurement of waist/hip circumference
- Bioelectrical impedance analysis (weight and body fat %)
- Measurement of blood pressure and heart rate
- Completion of the following self-report instruments: Food Craving Inventory, Food Preference Questionnaire, Eating Inventory
- Fasting serum glucose and insulin (no archiving)
- If participants will be using their own scale for at home weights during intervention, they will be asked to bring the scale in for calibration.

Weekly Intervention Visits (approximately 1.5 hours per visit)

The 12 weekly intervention visits will take place at Pennington Biomedical Research Center or virtually and they are designed to be specific to participants' random assignment, i.e., either the high-fat or the high-carbohydrate diet group. Body weight will be recorded by study staff at each of these 12 intervention visits. Additionally, participants will regularly weigh themselves at home (approximately once per day) and they will turn in a record of these self-measured weights at each weekly intervention visit. Participants will either be provided a loaner scale to use during the intervention or they will use their at home scale, calibrated by study staff at the Baseline visit.

The first intervention visit will be a one-on-one in person or virtual meeting with the interventionist following the baseline visit where participants will complete the Diet Personalization Survey. The next 11 intervention visits will be in person or virtual group meetings with other participants and a facilitator. The facilitator is a Pennington Biomedical Research Center staff member. Participants will receive personalized meal plans that are tailored to their calorie and (group-dependent) macronutrient target and they will include precise portion sizes of daily meals and snacks, a shopping list, and restaurant options. Two snacks per day (e.g., granola bar) will be provided by the sponsor, WW. The sponsor will further provide a food scale for each participant to facilitate adherence to the prescribed portion sizes.

Discussions and content delivered during the sessions will focus on helping participants adhere to their assigned diet. At the week 6 intervention visit, the Diet Personalization Survey will be completed.

Week 12 Clinic Visit: About 1.5 hours.

The visit will take place in the Outpatient Clinic at Pennington Biomedical Research Center. *This is a non-fasting visit.*

The visit will include the following procedures:

- Measurement of weight and waist/hip circumference
- Bioelectrical impedance analysis (weight and body fat %)
- Measurement of blood pressure and heart rate
- Completion of the following self-report instruments: Food Craving Inventory, Food Preference Questionnaire, Eating Inventory, Intervention Satisfaction Survey, Diet Personalization Survey
- If participants were loaned a scale for intervention, they will be asked to return it at this visit.

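### Clinic weight, impedance and waist/hip change compare a fasted baseline visit with a non-fasting week-12 visit, so absolute clinic weight loss is expected to be understated

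*Combined protocol and SAP*

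**What the plan says.** Under Study Procedures, the Baseline Clinic Visit is described thus: "This is a fasting visit (nothing to eat or drink before the visit, following a 12-hour fast". The Week 12 Clinic Visit carries the opposite instruction: "This is a non-fasting visit". Weight, impedance and waist/hip are measured at both visits. Table 2 schedules impedance and waist/hip at no other visit.

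Table 2 also suggests why the two visits differ. The row "Blood draw: fasting serum glucose, insulin" is marked at baseline only, so week 12 has no laboratory reason to fast.

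The Data analytic plan makes body weight change (kg and %) the primary outcome and analyses two sources, clinic weights and intervention-session weights. Of the first it says that "the presence of only two clinic weights means that analysis of the clinic weights will be a completers' analysis". It then adds: "Sensitivity analysis will be conducted to determine how the two methods effects the results". The covariates are the baseline value, sex and race, with further terms chosen by fit statistics such as AIC. The report to the sponsor is to contain "tables depicting change on the outcome variables and the associated inferential statistics".

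**The concern.** A participant weighed after 12 hours without food or drink carries less gut content and fluid, on average, than the same participant weighed without that restriction. With the restricted weighing first and the unrestricted one last, recorded loss is smaller than true loss on average.

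The planned model cannot remove this. Fasting state changes together with visit, so within an arm it cannot be separated from the passage of time. Adjusting for the baseline value does not help, because everyone's baseline is fasted. The documents do not provide for recording at week 12 who had eaten or drunk, so AIC has no such variable to select.

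Three things are at stake:

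- the absolute clinic weight loss per arm, which the plan commits to reporting;
- the change in impedance and waist/hip, which have no other source;
- the reading of any gap in absolute loss between the clinic and session series.

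**Working it through.** **Conditions side by side**

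| | Baseline clinic visit | Week-12 clinic visit |
|---|---|---|
| Food and drink | None, 12-hour fast | Non-fasting |
| Weight, impedance, waist/hip | Measured | Measured |
| Fasting blood draw | Yes | No |

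**Inputs from the Power analysis and Table 1.** Loss of 5.1 kg in a previous 12-week study, expected again in cells A and D. About half that in B and C: 5.1/2 = 2.55 kg. Planning SD 2.8 kg, difference 2.0 kg, mean body mass 90 kg. Cells of 52, 52, 25 and 25, so H1 compares 77 with 77.

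**Assumed inputs, not in the documents.** Mean offset d (food and fluid carried at week 12 but not at baseline) of 0.25 to 1.5 kg. Between-person SD of that offset of 0.5 to 1.0 kg.

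**Step 1: absolute loss.** Recorded loss = true loss − d. Share understated = d / true loss. In percentage points of body weight, d/90.

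| d (kg) | 5.1 kg recorded as | Understated | 2.55 kg recorded as | Understated | Points at 90 kg |
|---|---|---|---|---|---|
| 0.25 | 4.85 | 4.9% | 2.30 | 9.8% | 0.28 |
| 0.5 | 4.60 | 9.8% | 2.05 | 19.6% | 0.56 |
| 1.0 | 4.10 | 19.6% | 1.55 | 39.2% | 1.11 |
| 1.5 | 3.60 | 29.4% | 1.05 | 58.8% | 1.67 |

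**Step 2: between-diet contrasts.** With the same mean d in both diets, (5.1 − d) − (2.55 − d) = 2.55 kg in every row. In % the cancellation is nearly complete. If two groups' baseline means were as far apart as 90 and 95 kg (assumed), the remainder is 100 × d × (1/90 − 1/95), which is 0.03 points at d = 0.5 and 0.09 points at d = 1.5.

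**Step 3: precision.** Two-sample t-test, 2.0 kg, alpha 0.05. The plan's own figures first. At SD 2.8, H1 (77 vs 77) has two-sided power 0.993, in line with the stated value of over 0.95. A vs B (52 vs 52) has 0.950. C vs D (25 vs 25) has 0.697 two-sided and 0.801 one-sided, so the stated 0.80 is met there only one-sided. That is a separate matter and does not bear on this point.

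Adding the assumed noise: √(2.8² + 0.5²) = 2.844 and √(2.8² + 1.0²) = 2.973.

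| Comparison | SD 2.8 | SD 2.844 | SD 2.973 |
|---|---|---|---|
| C vs D, two-sided | 0.697 | 0.683 | 0.645 |
| C vs D, one-sided | 0.801 | 0.790 | 0.758 |
| A vs B, two-sided | 0.950 | 0.944 | 0.925 |
| H1, two-sided | 0.993 | 0.991 | 0.986 |

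The loss is about 0.01 to 0.05 for C vs D, under 0.03 for A vs B and under 0.01 for H1. It is smaller still if the 2.8 kg already contains such noise.

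**The case against.** The strongest reply is that every hypothesis is a randomised between-group contrast and none concerns absolute loss. That stands, and it limits the point to absolute change and its interpretation.

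A reader might go further and infer that H1 or H2 is biased because pre-visit intake could differ by diet. The documents give no basis for the existence, direction or size of such a difference, so this is not claimed. Nor would such an effect be confined to H2a and H2b. With Table 1's cell sizes, (52 − 25)/77 = 35% of a diet-specific offset would enter a pooled H1.

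Further objections, and what remains of each:

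- **The size is wholly assumed.** True. Non-fasting means that no fast is required, and no meal is prescribed. Some participants may arrive fasted, which lowers the mean offset but adds unrecorded variation. Confidence attaches to the mismatch, not to the range.
- **The clinic series may be only supporting.** Plausible: the repeated-measures model and the intent-to-treat analysis suit the session weights better. But the plan does not expressly rank the sources, and clinic weight is still analysed and reported.
- **The sensitivity analysis may concern only the contrasts.** If so, a common offset cancels there too. The difficulty arises only if absolute losses from the two sources are compared.
- **The session weights solve it.** The protocol states no fasting condition for them, so they cannot be assumed to be a matched series. A reader might equally infer that they are unreliable because sessions can be virtual and home scales used. The documents do not support that: staff record the weights, and participants' own scales are calibrated by staff at baseline.
- **Only baseline has a blood draw.** This explains the difference in instructions but does not make the body measurements comparable.

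**Conclusion.** The mismatch is explicit in the protocol, and confidence in it is high. If the plan is followed as written, absolute within-arm clinic weight loss is expected to be understated. The direction rests on participants carrying, on average, more food and fluid at an unrestricted visit than after a 12-hour fast. The amount is unknown. The 5% to 29% of 5.1 kg, and the 10% to 59% of 2.55 kg, are illustrations from an assumed offset, not estimates.

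For impedance and waist/hip, only non-comparability is claimed. H1, H2a and H2b are not shown to be biased, and their loss of precision is small under the assumed noise. This is a cheap improvement to consider, not a threat to the trial's main comparisons.

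**What to change.** Hold the week-12 clinic visit under the same fasting condition as the baseline clinic visit, so that weight, impedance and waist/hip are compared like for like.

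For participants already measured non-fasted, report the mismatch as a limitation of absolute clinic weight, impedance and waist/hip change. State in the analysis plan that a clinic-versus-session gap in absolute loss may partly reflect fasting state, in addition to the difference between a completers' and an intent-to-treat analysis.

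The cost is a changed visit instruction, a sentence in the analysis plan and one extra fast per participant. No new visit, procedure or staff is needed.
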